10.1.4.2 Evaluation of Non-Target Lesions

The distant control rate will be determined. Distant brain failure is defined as the radiographic appearance of a new or enhancing lesion more than 5 mm from the radiosurgical target volume[19]. Elsewhere brain failure rate will be determined using MRI scanning with gadolinium obtained at 3, 6, 9, and 12 months following SRS.

10.1.4.3 **Evaluation of Best Overall Response**

N/A

10.1.5 **Duration of Response**

N/A

10.1.6 **Progression-Free Survival (or other parameters)**

Time to progression will be measured from the time of SRS. Overall survival will be measured from 1) the time of diagnosis, and 2) time of SRS.

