3.1 Inclusion Criteria

- 3.1.1. All patients age 18 years and older with pathologically proven solid tumor malignancy and 1 to 4 brain metastases, one of which is 4.2 33.5 cm³.
- 3.1.2. Systemic therapy: Prior cytoxic systemic therapy must be completed \geq 5 days prior to radiosurgery. No concurrent cytoxic systemic therapy along with SRS. Cytoxic systemic therapy to start \geq 5 days after the completion of SRS.
- 3.1.3. Prior surgery or SRS is allowed as long as the target metastatic lesion in this study has not previously been treated with SRS.

- 3.1.4. Patient must exhibit the ability to understand and the willingness to sign a written informed consent.
- 3.1.5. Life expectancy of at least 12 weeks.

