4.1.3.2. Technical factors

Treatment shall be delivered using the Trilogy[™] Linear Accelerator (Varian Medical Systems, Palo Alto, CA) or the CyberKnife[™] Robotic Radiosurgery System (Accuray, Sunnyvale, CA).

4.1.3.3.Localization, simulation, and immobilization

The patient shall be treated in the supine position. An aquaplast head mask will be used to ensure adequate immobilization during therapy. The target volume shall be either the resection cavity or the unresectable lesion. When the resection cavity is targeted, a uniform isotropic 2 mm expansion of the cavity will be the target volume[17].

4.1.3.4.Critical structures

Critical normal structures (e.g., optic apparatus, brain stem) will be contoured and their doses minimized. The patient will be excluded from the protocol if the tumor's proximity to critical structures is such that a dosimetrically acceptable plan is not achievable to conform to these constraints.

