10. MEASUREMENT OF EFFECT

10.1 Anti-tumor Effect

Subjects will be seen in follow-up at 1, 3, 6, 9, and 12 months following SRS.At each follow-up, neurologic history and examination will be done. MRI with gadolinium will be obtained at 3, 6, 9, and 12 months.

10.1.1 **Definitions**

Early radiation toxicity is defined as those observed within 30 days of SRS. Late radiation toxicity is defined as those observed after 30 days following SRS. Tumor response will be measured using MRI with gadolinium obtained at 3, 6, 9 and 12 months following SRS.

10.1.2 **Disease Parameters**

Target lesion is defined as those treated with radiosurgery. The size and volume of the target lesion will be measured using the treatment planning software.

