10.1.4.1 Evaluation of Target Lesions

Radiographic response using MRI with gadolinium will be used. Follow-up MRI scans will be obtained at 3, 6, 9, and 12 months following SRS. Size of the treated lesion will be measured and compared to its pre-treatment size. Local tumor progression is defined as the radiographic appearance of a new or increasing enhancing lesion within the radiosurgical target volume. Local control is defined as lack of progression (P – below). Metabolic imaging may be necessary at times to distinguish tumor progression from treatment related radiation necrosis.

- 4.1.3.4.1. Complete response (CR): The tumor is no longer seen on the follow-up MRI scan.
- 4.1.3.4.2. Partial response (PR): Decrease of >50% in the product of two diameters on the follow-up MRI scan.

- 4.1.3.4.3. Minor response (MR): Decrease of <50% in the product of two diameters on the follow-up MRI scan.
- 4.1.3.4.4. Stable disease (SD): The scan shows no change.
- 4.1.3.4.5. Progression (P): A >25% increase in tumor area (product of two diameters).

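### Read literally, the distant brain failure definition counts an enhancing metastasis present at entry and not treated with study SRS, even if it is stable or shrinking

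*Combined protocol and SAP*

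**What the plan says.** Section 10.1.4.2 (Evaluation of Non-Target Lesions) gives the only definition of distant brain failure: "the radiographic appearance of a new or enhancing lesion more than 5 mm from the radiosurgical target volume". It is assessed on MRI at 3, 6, 9 and 12 months. Distant brain control is a named secondary endpoint (1.2.3 and 12.1.2.2).

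The neighbouring section, 10.1.4.1, defines local progression as the appearance of "a new or increasing enhancing lesion within the radiosurgical target volume". It compares the size of the treated lesion with its pre-treatment size, and its category P sets a threshold: an increase of more than 25% in the product of two diameters.

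Several other passages decide which lesions the distant rule can reach:

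- Section 3.1.1 admits patients with "1 to 4 brain metastases, one of which is" between 4.2 and 33.5 cm³.
- Section 3.1.3 adds: "Prior surgery or SRS is allowed as long as the target metastatic lesion in this study has not previously been treated with SRS".
- Section 10.1.2 says: "Target lesion is defined as those treated with radiosurgery".
- Section 4.1.3.3 says: "The target volume shall be either the resection cavity or the unresectable lesion".
- Sections 4.4 and 9 schedule a pre-treatment MRI.

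**The concern.** In the distant rule, *enhancing* stands as an alternative to *new*, with nothing that requires change. A lesion that is not new but takes up contrast therefore satisfies the wording. Patients may enter with other metastases, and these may still enhance at the first follow-up scan without having progressed. The local rule has the missing word, *increasing*, so the two definitions differ on the feature that separates progression from persistence.

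At stake is the distant control rate, which would be biased downwards by an amount that depends on disease already present at entry. There could also be a knock-on effect. Section 4.4 ties the MRI schedule to documentation of progression, section 4.5 lists disease progression among the reasons for removal, and section 10.1.6 measures time to progression. If a distant failure is taken as progression in those sections, a false one would carry over into them.

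**Working it through.** The plan states no figure for distant control and bases no sample size on it, so there is nothing to reproduce. The check is a comparison of texts, followed by a bound.

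**Step 1: the two definitions side by side.**

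| Feature | Local (10.1.4.1) | Distant (10.1.4.2) |
|---|---|---|
| Word requiring change | *increasing* | none |
| Growth threshold | >25% in product of two diameters (P) | none |
| Comparison with pre-treatment size | yes | none |

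**Step 2: which lesions are exposed.** Of 1 to 4 metastases, only one must be in the study size range, so up to 4 − 1 = 3 others may be present. For one of these to become a failure at 3 months without having progressed, it must:

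1. not be treated with SRS in the study (left untreated, or treated before entry);
2. lie more than 5 mm from the target volume; and
3. still enhance at the 3-month MRI.

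Nothing in the documents exempts lesions present at entry, and nothing says that every such lesion receives study SRS.

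**Step 3: the bound.** Let m be the share of patients with at least one lesion meeting all three conditions. Each is recorded as a failure at the first scan and stays one. Hence

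reported distant control ≤ 1 − m.

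**Step 4: illustration.** Let C be the true 3-month distant control. Neither C nor m is in the documents; C = 80% and the values of m are assumptions. If the two are independent, reported control = (1 − m) × C. If patients with such lesions are also likelier to fail truly (positive dependence), the two kinds of failure overlap and reported control lies between that product and the smaller of C and 1 − m.

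| m | (1 − m) × C | Upper end, min(C, 1 − m) |
|---|---|---|
| 0% | 1.00 × 0.80 = 80% | 80% |
| 10% | 0.90 × 0.80 = 72% | 80% |
| 25% | 0.75 × 0.80 = 60% | 75% |
| 50% | 0.50 × 0.80 = 40% | 50% |

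**Step 5: weight of one patient.** Section 12.3.1 gives a maximum of 30 evaluable subjects per arm. One misclassified patient moves that arm's rate by 1/30 = 3.3 percentage points, and by more in a smaller arm.

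**The case against.** There are three serious counter-arguments.

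*The defined event is an appearance.* A lesion already on the pre-treatment MRI does not appear at 3 months, and the parallel phrasing in 10.1.4.1 suggests that a word was simply dropped. That is a plausible account of the intent. But if *appearance* means emergence, *enhancing* adds nothing to *new*, and growth of a known untreated metastasis would never count. Either reading leaves the text in need of an edit. Section 10.1.7 marks response review as not applicable, so no written procedure secures a common reading.

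*Other metastases may be treated in the same course.* Section 10.1.2 makes lesions treated with radiosurgery target lesions, and 10.1.4.2 concerns non-target lesions. Section 2.4 describes a practice of using SRS for a limited number of metastases, and section 8.1 computes dosimetry for each lesion. This stands as a real limit: co-treated lesions may escape the rule and m could be near zero. It is not conclusive, because 4.1.3.3 and 10.1.4.2 speak of a single target volume and no section says that all baseline metastases receive study SRS. Section 10.1.2 also does not say whether SRS given before entry makes a lesion a target lesion. If it does, the exposed group shrinks further.

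*The endpoint is descriptive.* No test, threshold or sample size rests on distant control. That is correct and limits the severity.

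A reader might infer that every patient with more than one metastasis fails at the first MRI, or that the distant control rate would mainly count how many patients had several lesions at entry. The documents do not support either. They give no distribution of lesion number, no share left without SRS and no distant control rate, and the three conditions above all have to be met.

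**Conclusion.** The definition is defective as written. It has no growth requirement, no threshold and no baseline reference, and no other section supplies them. Followed literally, it classifies some stable or shrinking disease as distant failure.

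The size of the error cannot be determined from the documents. The firm result is that reported control cannot exceed 1 − m. The illustrative values depend on the assumed C and m and, for the product, on independence; with positive dependence the loss is smaller. If nearly all baseline metastases are study SRS targets and *the radiosurgical target volume* covers each of them, the effect is close to nil.

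One secondary endpoint is affected. The MTD, the DLT definition and the escalation rule do not use distant failure. The correction is worth making because it is cheap and the endpoint is otherwise open to two readings.

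**What to change.** In 10.1.4.2, define distant brain failure as either of the following, located more than 5 mm from any target volume treated with SRS in the study:

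- a lesion absent from the pre-treatment MRI; or
- an increase of more than 25% in area (product of two diameters, criterion P of 10.1.4.1) of a pre-existing non-target lesion, compared with the pre-treatment MRI.

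Name criterion P explicitly, because 10.1.4.1 also contains the looser descriptive wording without a threshold. State that a non-target lesion is any metastasis on the pre-treatment MRI that is not treated with SRS in the study, including one treated before entry, and that the target volume covers every site treated in the study course. List the baseline non-target lesions for each patient from the pre-treatment MRI.

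The same edit can assign enhancing lesions that lie outside the target volume but within 5 mm of it, which at present are neither local nor distant failures.

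The cost is small: a revised definition, a baseline lesion list, and two-diameter measurements of those lesions. No additional scan is needed, since the pre-treatment and follow-up MRIs are already scheduled.

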10.1.7 Response Review

N/A

10.2 Other Response Parameters

The primary endpoint of this study is to determine the MTD of tri-fraction SRS. The MTD is defined as one dose level below the highest toxic dose (i.e., the DLT dose). Similar to RTOG 90-05, the dose limiting toxicity (DLT) is defined as grade 3, 4, or 5 RTOG central nervous system (CNS) acute radiation morbidity scoring criteria (Appendix C) observed within 30 days of radiosurgery.

The occurrence of late toxicities will be continuously monitored. If a late DLT occurs in 3 or more out of 6 (or 4 or more out of 12) patients at a certain dose level after the radiation dose had already been escalated to the next level, the MTD will be backtracked to the level

below the one at which the DLTs occurred.

11. DATA REPORTING / REGULATORY CONSIDERATIONS

11.1 Monitoring plan

Stanford Cancer Center (SCC) Data and Safety Monitoring Committee (DSMC) will be responsible for monitoring the research yearly and will operate independently from the clinical investigators. The primary responsibility of the DSMC is to review the reported study data to confirm it is accurate, complete, and verifiable from source documents. The DSMC will also confirm that the conduct of the trial maintains the safety and well being of human subjects, and is in compliance with the currently approved protocol, with GCP, and with applicable regulatory requirements. Study safety data will be reviewed by the DSMC in the form of summary reports or data listings on a regular basis.

11.2 Stopping rules (for the individual patient and for the study as a whole)

The dose limiting toxicity (DLT) is defined as grade 3, 4, or 5 RTOG central nervous system (CNS) acute radiation morbidity scoring criteria (Appendix C) observed within 30 days of radiosurgery.

The occurrence of late toxicities will be continuously monitored. If a late DLT occurs in 3 or more out of 6 (or 4 or more out of 12) patients at a certain dose level after the radiation dose had already been escalated to the next level, the MTD will be backtracked to the level below the one at which the DLTs occurred.

Number of Patients at a Given Dose Level with a DLT	Escalation Decision Rule
0-1 out of 6	Enter 6 patients at the next higher dose level
2 out of 6	 Enter at least 6 more patients at the current dose level. If 0-1 of these 6 experience a DLT (i.e., 2-3 out of 12), then proceed to next dose level. If 2 or more of these 6 experience a DLT (4 or more out of 12), then dose escalation will be stopped. Six additional patients will be entered at the next lower dose level if only 6 patients were previously entered.

Does escalation will proceed as follows:

3 or more out of 6	Dose escalation will be stopped. Six additional
	patients will be entered at the next lower dose level if
	only 6 patients were previously entered.

Should a patient not be evaluable at 30 days (due to death or loss to follow-up or discontinuation of the protocol follow-up per patient preference), then additional patients may be enrolled on each arm such that at least 5 of 6 are evaluable and experience no DLT. For example, should one patient be lost to follow up, but the remaining 5 patients have no DLT, then dose escalation may proceed.

11.3 Data management

All data files (contains patients' names, medical record numbers, treatment, and follow-up information) for this study will be kept in a secure office in the department of Neurosurgery and Radiation Oncology. The electronic data file for this study, which contains patients' names, medical record numbers, treatment, and follow-up information, is kept under password protection.

11.4 Confidentiality

All signed informed consents and data files (contains patients' names, medical record numbers, treatment, and follow-up information) for this study will be kept in a secure office in the department of Neurosurgery and Radiation Oncology. The electronic data file for this study, which contains patients' names, medical record numbers, treatment, and follow-up information, is kept under password protection.

12. STATISTICAL CONSIDERATIONS

12.1 Endpoints

12.1.1 Primary endpoint

Determine the maximum tolerated dose (MTD) of SRS given in 3 fractions for brain metastases 4.2 - 14.1 cm³ and 14.2 - 33.5 cm³.

12.1.2 Secondary endpoints

- 12.1.2.1.To determine the local control rate of fractionated SRS for brain metastases $4.2 14.1 \text{ cm}^3$ and $14.2 33.5 \text{ cm}^3$.
- 12.1.2.2.To determine the distant brain control rate of fractionated SRS for brain metastases 4.2 14.1 cm³ and 14.2 33.5 cm³.
- 12.1.2.3.To determine the overall survival rate of fractionated SRS for brain metastases 4.2 14.1 cm³ and 14.2 33.5 cm³.

- 12.1.2.4.To determine the short- and long-term adverse effects of fractionated SRS for brain metastases 4.2 14.1 cm³ and 14.2 33.5 cm³.
- 12.1.2.5.Patient health related quality of life will be assessed using the EORTC QLQ-C30 and EORTC Brain Cancer Module QLQ-BN20.

12.2 Analysis Populations

Each of the four arms will be analyzed separately to determine the MTD for each arm.

Arm	
1	4.2 - 14.1 cm ³ brain metastasis following surgical resection
2	14.2 - 33.5 cm ³ brain metastasis following surgical resection

There will be no subset analysis.

12.3 Sample Size

12.3.1 Accrual estimates

Six subjects per group will be enrolled at the starting dose for each of the four arms. Should a patient not be evaluable at 30 days (due to death or loss to follow-up or discontinuation of the protocol follow-up per patient preference), then additional patients may be enrolled on each arm such that at least 5 of 6 experience no DLT. The maximum number of subjects per arm will depend on the number of dose levels reached. If all four dose levels are reached, the maximum number of evaluable subjects in each arm is 30. If all four dose levels are reached for the all two arms of the study, the maximum number of subjects for the entire study is 60.

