	$14.2 - 33.5 \text{ cm}^3$.
	• Patient health related quality of life
	will be assessed.
SAMPLE SIZE BY TREATMENT	If all four dose levels are reached, the
GROUP	maximum number of evaluable subjects in each arm is 30: therefore the maximum
	number of subjects for the entire study is 60.
SUMMARY OF SUBJECT ELIGIBILITY	Inclusion Criteria
CRITERIA	• All patients age 18 years and older with
	pathologically proven solid tumor
	malignancy and 1 to 4 brain metastases,
	one of which is $4.2 - 33.5$ cm ³ .
	• Systemic therapy: Prior cytoxic systemic
	therapy must be completed ≥ 5 days prior
	to radiosurgery. No concurrent cytoxic
	systemic therapy along with SRS. Cytoxic
	systemic therapy to start ≥ 5 days after the
	completion of SKS.
	 Prior surgery or SRS is allowed as long as the target metastatic locian in this study has
	not provide hear treated with SPS
	• Detions much avhibit the ability to
	• Patient must exhibit the ability to
	written informed consent
	• Life expectancy of at least 12 weeks
	• Ene expectancy of at least 12 weeks.
	Exclusion Criteria
	• Patients who have previously been treated
	with whole brain irradiation.
	• Patients whose metastatic lesion in
	question had previously been treated with
	SRS.
	• The patient has greater than 4 total brain
	metastases at the time of initial evaluation.

	• Pediatric patients (age <18), pregnant
	women, and patients who are unable to
	give informed consent will be excluded.
INVESTIGATIONAL PRODUCTS	N/A
DOSAGE AND ADMINISTRATION	
CONTROL GROUP	N/A
PROCEDURES	N/A
STATISTICAL CONSIDERATIONS	6+6 design for dose escalation

SCHEMA

Arm	Metastasis Size (cm ³)	Surgical Candidate?	Treatment
1	4.2 - 14.1	Yes	Surgery \rightarrow SRS
2	14.2 - 33.5	Yes	Surgery \rightarrow SRS

Dose Level	Dose Per Fraction	Total Dose
1	8 Gy	24 Gy
2	9 Gy	27 Gy
3	10 Gy	30 Gy
4	11 Gy	33 Gy

AE	Adverse event
CNS	Central nervous system
CR	Complete response
CRF	Case report/Record form
CTCAE	Common Terminology Criteria for Adverse Events
DLT	Dose Limiting Toxicity
DSMB	Data Safety Monitoring Board
IRB	Institutional Review Board
IV	Intravenous
KPS	Karnofsky Performance Scale
MR	Minor response
OS	Overall survival
Р	Progression (disease)
PD	Protocol Director
PFS	Progression free survival
PR	Partial response
QD	Once daily
RECIST	Response evaluation criteria in solid tumors
SAE	Serious adverse event
SD	Stable disease
SRS	Stereotactic Radiosurgery
WBRT	Whole Brain Radiation

LIST OF ABBREVIATIONS AND DEFINITION OF TERMS

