4.1.3. RADIATION THERAPY

4.1.3.1.Dose specifications/escalation

SRS will be delivered in 3 fractions. Provided that the MTD has not been reached, the total dose will be increased in 3 Gy increments:

Dose Level	Dose Per Fraction	Total Dose
1	8 Gy	24 Gy
2	9 Gy	27 Gy
3	10 Gy	30 Gy
4	11 Gy	33 Gy

A minimum of six patients will be enrolled per arm:

Arm	
1	4.2 - 14.1 cm ³ brain metastasis following surgical resection
2	14.2 - 33.5 cm ³ brain metastasis following surgical resection

Similar to RTOG 90-05, the dose limiting toxicity (DLT) is defined as grade 3, 4, or 5 RTOG central nervous system (CNS) acute radiation morbidity scoring criteria (Appendix C) observed within 30 days of radiosurgery. The MTD is defined as one dose level below the highest toxic dose (i.e., the DLT dose).

The occurrence of late toxicities will be continuously monitored. If a late DLT occurs in 3 or more out of 6 (or 4 or more out of 12) patients at a certain dose level after the radiation dose had already been escalated to the next level, the MTD will be backtracked to the level

below the one at which the DLTs occurred.

Number of Patients at a Given	Escalation Decision Rule					
Dose Level with a DLT						
0-1 out of 6	Enter 6 patients at the next higher dose level					
2 out of 6	Enter at least 6 more patients at the current dose level.					
	• If 0-1 of these 6 experience a DLT (i.e., 2-3					
	out of 12), then proceed to next dose level.					
	• If 2 or more of these 6 experience a DLT (4 or more out of 12), then dose escalation will be stopped. Six additional patients will be entered at the next lower dose level if only 6 patients were previously entered.					
3 or more out of 6	Dose escalation will be stopped. Six additional patients will be entered at the next lower dose level if only 6 patients were previously entered.					

Does escalation will proceed as follows, with minimum waiting period of 30 days before proceeding with the next higher dose level:

Should a patient not be evaluable at 30 days (due to death or loss to follow-up or discontinuation of the protocol follow-up per patient preference), then additional patients may be enrolled on each arm such that at least 5 of 6 are evaluable and experience no DLT. For example, should one patient be lost to follow up, but the remaining 5 patients have no DLT, then dose escalation may proceed.

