12.3.2 Sample size justification

The sample size will be determined by the number of dose levels reached.

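### The stated maximum of 30 evaluable subjects per arm and 60 overall does not follow from the escalation table, which allows 48 and 96 with exactly 6 patients per expansion

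*Combined protocol and SAP*

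**What the plan says.** Section 12.3.1 gives the per-arm figure ("If all four dose levels are reached, the maximum number of evaluable subjects in each arm is 30") and then the two-arm total: "the maximum number of subjects for the entire study is 60". The synopsis repeats the per-arm figure ("maximum number of evaluable subjects in each arm is 30") and the total. No derivation is shown. Section 12.3.2 says only: "The sample size will be determined by the number of dose levels reached".

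The escalation table appears in sections 4.1.3.1 and 11.2 and is worded for any given dose level:

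- 0 or 1 DLT in 6: open the next level with 6 patients.
- 2 DLTs in 6: "Enter at least 6 more patients at the current dose level". Then: "If 0-1 of these 6 experience a DLT (i.e., 2-3 out of 12), then proceed to next dose level". With 4 or more in 12, escalation stops.
- 3 or more DLTs in 6: escalation stops.
- After either kind of stop: "Six additional patients will be entered at the next lower dose level if only 6 patients were previously entered".

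Both sections also allow a cohort to clear with one non-evaluable patient: "should one patient be lost to follow up, but the remaining 5 patients have no DLT, then dose escalation may proceed".

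**The concern.** The table can expand a level and still escalate, and nothing restricts this to one level per arm. An arm that follows the rule exactly can therefore pass the number that the plan calls its maximum.

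What is at stake is the planned size of the study and the meaning of the figure. No section makes 30 or 60 an enrolment cap, and section 12.3.2 lets the levels reached decide the size, so a misstated planning maximum is the better-supported reading. The word still leaves a cap reading open. In that case the plan does not say what happens, or how an MTD is declared, if an arm reaches 30 before the rule has finished.

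**Working it through.** **Inputs from the plan.** Four dose levels; 6 patients in each first cohort; at least 6 more after 2 of 6; escalation allowed after 2 to 3 of 12; back-fill of 6 at the next lower level after a stop if only 6 were entered there; two arms in the study total. I take each expansion as exactly 6 and each cohort as full.

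**Step 1: the plan's own figure.**
- 4 x 6 + 6 = 30 per arm, and 2 x 30 = 60. This is 6 per level plus one expansion or one back-fill in the whole arm.
- Without any extra cohort, 4 x 6 = 24.

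**Step 2: what the table allows.**
- Each level ends with 6 or 12 patients. An arm that reaches level 4 therefore has 24 + 6k patients, k = 0 to 4: 24, 30, 36, 42 or 48.
- Maximum: 4 x 12 = 48 per arm and 2 x 48 = 96 for the study.
- Because the table says at least 6, even 48 is a ceiling only if the expansion size is fixed.

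**Step 3: short paths past 30.**
- Two expansions: 24 + 6 + 6 = 36.
- No expansion at levels 1 to 3, then 2 of 6 and 4 or more of 12 at level 4, then back-fill of level 3: 6 + 6 + 12 + 12 = 36.
- An arm that stops at level 3 can also need 3 x 12 = 36, although the sentence in 12.3.1 covers only arms that reach level 4.

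**Step 4: how often.** The plan gives no DLT rates, so every rate here is an assumption. At a level with DLT probability p:
- a = P(0 or 1 of 6) = (1-p)^6 + 6p(1-p)^5
- c = P(2 of 6) = 15p^2(1-p)^4
- escalate with 6: a; escalate with 12: ca; stop with 6: 1 - a - c; stop with 12: c(1-a).

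At p = 0.20 for all levels, a = 0.6554 and c = 0.2458. Summing all paths gives P(36) = 0.1247, P(42) = 0.0276 and P(48) = 0.0025, so P(more than 30) = 0.155.

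P(48) has two parts. Either levels 1 to 3 all expand and level 4 takes 12, or levels 1 and 2 expand, level 4 stops at 12 and level 3 is back-filled:

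(ca)^3 c + (ca)^2 a c(1-a) = 0.00103 + 0.00144 = 0.00247.

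The last column below takes the two arms as independent with the same curve.

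| Assumed DLT rate by level (%) | P(arm >30) | P(arm >30, given level 4 reached) | P(arm >36) | P(arm = 48) | P(two arms >60) |
|---|---|---|---|---|---|
| 5 flat | 0.006 | 0.006 | 0.0002 | <0.00001 | 0.002 |
| 10 flat | 0.052 | 0.055 | 0.004 | 0.0001 | 0.036 |
| 15 flat | 0.121 | 0.152 | 0.017 | 0.0010 | 0.106 |
| 20 flat | 0.155 | 0.264 | 0.030 | 0.0025 | 0.128 |
| 25 flat | 0.136 | 0.364 | 0.031 | 0.0030 | 0.088 |
| 30 flat | 0.090 | 0.439 | 0.021 | 0.0023 | 0.040 |
| 2/5/10/20 | 0.107 | 0.110 | 0.003 | 0.00002 | 0.083 |
| 5/10/15/20 | 0.133 | 0.149 | 0.012 | 0.0003 | 0.125 |
| 5/10/20/30 | 0.215 | 0.268 | 0.021 | 0.0005 | 0.243 |
| 10/15/20/30 | 0.239 | 0.321 | 0.040 | 0.0021 | 0.264 |
| 10/20/30/40 | 0.196 | 0.412 | 0.035 | 0.0020 | 0.201 |
| 15/20/25/30 | 0.208 | 0.374 | 0.043 | 0.0033 | 0.201 |

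P(two arms >72) is at most 1.9%, and P(96) is at most 1.1 in 100,000.

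**Step 5: can replacements explain 30?** No. Replacing a non-evaluable patient adds an enrolled patient, not an evaluable one, and 30 is stated as evaluable. The 60 is labelled subjects but equals 2 x 30 evaluable, so replacements would raise enrolment further.

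**The case against.** The figure sits under a heading about accrual estimates, no test or power depends on it, and no section stops enrolment at 30 or 60. Expected size under the 12 curves is about 18 to 29 per arm, below 30 in every case, so 30 works as a budget figure. The 48-patient path is very rare, and 76% to 97% of overruns stop at 36. Nor is 48 a strict ceiling while the table says at least 6.

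Most of this stands, and it limits the weight of the point. The decision rule is sound as it is, and the practical gap is usually one cohort. It does not rescue the number: both places call 30 a maximum, and the table exceeds it on ordinary paths. The last remark is a reason to write the expansion size next to the restated figure, not a reason to keep 30.

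One could also object that the unconditional probabilities do not match a sentence that is conditional on reaching all four levels. Conditioning makes an overrun more likely, for example 26% instead of 15% at a flat 20%.

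**Conclusion.** The concern holds. Thirty and 60 are not the maxima under the escalation table. With exactly 6 patients per expansion or back-fill, the maxima are 48 per arm and 96 for two arms; with the table's open-ended wording there is no upper limit. Under the assumed curves, an arm passes 30 with probability 0.6% to 24% (0.6% to 44% among arms that reach level 4), and two arms together pass 60 with probability 0.2% to 26%. These ranges rest wholly on assumed DLT rates. The escalation decisions and the MTD definition are unaffected. This should be corrected, but it does not undermine the design.

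**What to change.** In section 12.3.1 and the synopsis, state that with all four levels reached the maximum is 48 evaluable subjects per arm and 96 for two arms, assuming exactly 6 patients per expansion or back-fill, with replacements for non-evaluable patients in addition. Reconcile that assumption with the open-ended wording of the table in 4.1.3.1 and 11.2. Do not present 24 as a minimum, since a cohort may clear with 5 evaluable patients.

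If 30 and 60 are meant as an enrolment cap, say so, and say how the MTD is reported when the cap is reached before the rule finishes.

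As a side point, sections 12.2 and 12.3.1 refer to four arms while two are listed, and sections 4.1.2 and 4.1.3.3 still provide for unresected lesions. The total of 60 uses two arms, so the result here does not change, but the passages should be reconciled because the study total scales with the number of arms.

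The cost is low: one planning figure is restated in two places with its assumption. The escalation decisions need not change, but the declared maximum size becomes larger.
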